	
• Lipid status: Total cholesterol, triglycerides, high-density lipoprotein (HDL) and low-density lipoprotein (LDL)• Stimulation tests:
• Two different growth hormone (GH) stimulation tests, chosen from the following: a) insulin tolerance test (with cortisol response to hypoglycemia), b) arginine test, c) clonidine test, d) glucagon test (with or without propranolol, with cortisol response, unless cortisol measured during an intent-to-treat (ITT)), or e) L-dopa test (with or without propranolol)• Sex hormone priming is suggested (but not required) to be performed prior to GH stimulation tests for girls over the age of 10 and boys over the age of 11• If 1 or both of the stimulation tests have been performed within approximately 6 months prior to Screening and have been well documented (with a proper recording of sample timing and results as well as euthyroid status of the subject) it may be accepted. In accordance with recent Guidelines, in subjects with known panhypopituitarism (eg, subjects who are deficient in TSH and/or ACTH post cranial radiation), GH stimulation tests may not be required in subjects who meet all other inclusion criteria and whose history is consistent with GHD including low growth velocity, low IGF-1 and IGFBP-3 levels, and delayed bone age. Also in children who are born panhypopituitary with deficiency of ≥ 2 pituitary hormones in addition to GH, do not require stimulation tests. The final decision rests with the Medical Expert• In case the subject was not previously assessed for deficiencies of the hypothalamus-pituitary-adrenal axis (HPA), competence should be demonstrated by an 8:00 AM cortisol > 190 nmol/L (7 $\mu\text{g/dL}$) in subjects with idiopathic GHD only, or by a peak cortisol level ≥ 500 nmol/L (18 $\mu\text{g/dL}$) in the context of an insulin tolerance test or glucagon stimulation test. At the discretion of the investigator, or in case Screening results are borderline or not interpretable (eg, from insulin tolerance test) or raising concerns, a Standard Dose or Low Dose Short adrenocorticotrophic hormone (ACTH) test should be conducted
--	--

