- 8) Children with multiple hormonal deficiencies must be on stable replacement therapy (stable dose and normal blood hormone levels) for other hypothalamo-pituitary axes for approximately 3 months. Thyroid replacement therapy for thyroid hormone deficiency must be instituted approximately 6 months (and be stable for approximately 3 months) prior to Screening. Temporary adjustment of glucocorticoid replacement therapy, as appropriate, is acceptable.
- 9) Normal 46 XX karyotype for girls (results prior to Screening may be accepted)
- 10) Written, signed informed consent of the parent(s) or legal guardian(s) of the subject and written assent of the subject (if the subject is able to read, understand, and sign)

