 - Two different GH stimulation tests, chosen from the following: a) insulin tolerance test (with cortisol response to hypoglycemia), b) arginine test, c) clonidine test, d) glucagon test (with or without propranolol, with cortisol response unless cortisol measured during an ITT), or e) L-dopa test (with or without propranolol)
 - Sex hormone priming is suggested (but not required) to be performed prior to GH stimulation tests for girls over the age of 10 and boys over the age of 11

- If 1 or both of the stimulation tests have been performed within approximately 6 months prior to Screening and have been well documented (with a proper recording of sample timing and results as well as euthyroid status of the subject) it may be accepted. In accordance with recent Guidelines, in subjects with known panhypopituitarism (eg, subjects who are deficient in TSH and/or ACTH post cranial radiation), GH stimulation tests may not be required in subjects who meet all other inclusion criteria and whose history is consistent with GHD including low growth velocity, low IGF-1 and IGFBP-3 levels, and delayed bone age (*Grimberg 2016*). Also in children who are born panhypopituitary with deficiency of ≥ 2 pituitary hormones in addition to GH, do not require stimulation tests. The final decision rests with the Medical Expert
 - In case the subject was not previously assessed for deficiencies of the HPA, competence should be demonstrated by an 8:00 AM cortisol > 190 nmol/L (7 $\mu\text{g/dL}$) in subjects with idiopathic GHD only, or by a peak cortisol level ≥ 500 nmol/L (18 $\mu\text{g/dL}$) in the context of an insulin tolerance test or glucagon stimulation test. At the discretion of the investigator, or in case Screening results are borderline or not interpretable (eg, from insulin tolerance test) or raising concerns, a Standard Dose or Low Dose Short ACTH test should be conducted
- 9) Karyotype testing to rule out Turner Syndrome will be performed in all female subjects (results obtained prior to Screening may be accepted if well documented; the final decision rests with the Medical Expert)
- 10) Sellar MRI: contrast dye is recommended (if not conducted within approximately 6 months prior to Screening); performed and read locally
- 11) Fundoscopy (to rule out papilledema or signs of intracranial hypertension or mass effect)

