- ⁶ 8:00 AM cortisol (eg, baseline for GH stimulation test) < 7 µg/dL requires an ACTH stimulation test. 8:00 AM cortisol ≥ 7 µg/dL satisfies inclusion. This assessment may be performed prior to Screening within approximately 3 months with proper documentation and approval by the Medical Expert.
- ⁷ These assessments may be performed prior to Screening within approximately 3 months with proper documentation and approval by the Medical Expert.
- ⁸ Karyotype evaluation in girls. Results prior to Screening may be accepted if well documented; the final decision rests with the Medical Expert.
- ⁹ Subjects should rest for at least 2 minutes before ECG assessment. Screening ECG is locally read; all other ECGs to be read centrally.
- ¹⁰ At predose and 8, 12, 16, 24, 36, 48, 72, 96, 120 and 168 h postdose for TransCon hGH PK/PD subset subjects.
- ¹¹ Should be performed at any time if clinically indicated.
- ¹² Hematology (blood smears will be performed locally for back-up analysis), blood chemistry, lipid and glucose metabolism (fasting glucose, insulin, HbA1c, and OGTT can be assessed locally at any time in case of suspicion of glucose intolerance).
- ¹³ Hormone status: TSH, fT3, fT4, and morning cortisol.
- ¹⁴ Bioanalytical samples for TransCon hGH, hGH, PEG, IGF-1 and IGFBP-3: IGF-1 and PEG will be analyzed at screening and V1 through V6. TransCon hGH, hGH, and IGFBP-3 analysis only at V1 to V6. Screening PEG levels only to be analyzed after randomization.
- ¹⁵ The analysis of the anti-hGH and anti-PEG antibodies may only be conducted after randomization and are not required for eligibility verification.
- ¹⁶ Only for TransCon hGH PK/PD subset subjects.
- ¹⁷ Training on study drug preparation and administration (V1 - during first administration and further as needed).
- ¹⁸ At 15 min, 1 h and 2 h postdose.
- ¹⁹ At 15 min, 1 h, 2 h and 24 h postdose for TransCon hGH PK/PD subset subjects; time point for other subjects as they attend to site.

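### For a child not previously assessed for HPA deficiency, Schedule footnotes 6 and e accept a morning cortisol whatever the cause of GHD; the Synopsis and 10.1.1 accept it in idiopathic GHD only

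*Protocol*

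**What the plan says.** The Protocol states the adrenal check in two forms, both current text.

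**Schedules of Events (17.2, footnote 6; 17.3, footnote e).** Both footnotes are attached to the row for adrenal status. A morning value below 7 µg/dL "requires an ACTH stimulation test. 8:00 AM cortisol" of 7 µg/dL or more "satisfies inclusion. This assessment may be performed prior to Screening within approximately 3 months with proper documentation and approval by the Medical Expert". The wording is the same for both arms. The cause of GHD is not mentioned, and the companion footnotes 7 and f add no limit.

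**Synopsis (Screening Period) and 10.1.1.** The rule has a stated scope: "In case the subject was not previously assessed for deficiencies of the HPA, competence should be demonstrated by an 8:00 AM cortisol" above 190 nmol/L (7 µg/dL) "in subjects with idiopathic GHD only, or by a peak cortisol level" of at least 500 nmol/L (18 µg/dL) in an insulin tolerance or glucagon test. An ACTH test has its own triggers: "At the discretion of the investigator, or in case Screening results are borderline or not interpretable", "or raising concerns, a Standard Dose or Low Dose Short ACTH test should be conducted".

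**Numbered entry criteria (8.1.1 and 8.1.2).** None contains a cortisol threshold. The nearest is inclusion criterion 8: "Children with multiple hormonal deficiencies must be on stable replacement therapy (stable dose and normal blood hormone levels", which concerns known multiple deficiencies.

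**The concern.** The two forms can send the same child down different routes. Under 10.1.1, a morning cortisol alone is not enough when GHD has a known organic cause. Under the footnotes it is enough for everyone.

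What is at stake is the adequacy of a paediatric safety work-up before growth hormone is started. The Protocol itself links the two: 9.9.2.1 notes that growth hormone may increase conversion of hydrocortisone to cortisone and lets the investigator raise the replacement dose. A site working from the schedule table could finish screening without the stimulated cortisol that 10.1.1 calls for. The footnotes can also impose an ACTH test on a child whom 10.1.1 already regards as competent.

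**Working it through.** No sample size, power or error-rate figure is involved, so the check compares the two rules case by case.

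**1. Can the affected child be enrolled?** Yes.
- Inclusion criterion 1 admits GHD that is isolated or part of a multiple deficiency and does not require an idiopathic cause.
- SAP 8.5 plans an isolated organic subgroup: no other axis deficient, but a history of brain irradiation or a relevant abnormal MRI. Criterion 8 does not reach these children.
- A stimulated cortisol is not guaranteed. In 10.1.1, two of the five permitted GH stimulation tests (insulin tolerance and glucagon) carry a cortisol response. The two required tests may instead come from arginine, clonidine and L-dopa, for which none is specified.

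**2. Is the difference between > and ≥ a real conflict?** No.
- 10.1.1 pairs 500 nmol/L with 18 µg/dL: 500 / 18 = 27.8 nmol/L per µg/dL.
- It pairs 190 nmol/L with 7 µg/dL: 190 / 7 = 27.1. The two factors differ, so there is rounding in the pairings.
- With the first factor, 7 × 27.8 ≈ 194 nmol/L, which is above 190 and passes 10.1.1. The 500/18 pairing is itself rounded, so this is an indication, not a proof. The difference is treated as unit rounding and left out.

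**3. Rule comparison for a child not previously assessed.**
- Footnote rule: cleared if the morning value is at or above the cut-off; otherwise an ACTH test is required.
- 10.1.1 rule: cleared if (idiopathic and morning value above the cut-off) or a qualifying stimulated peak exists. Its ACTH route is left out of this step.
- Cases: 2 causes × 2 morning levels × 2 peak states = 8.

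| Cause | Morning cortisol | Qualifying peak | Footnote | 10.1.1 | Result |
|---|---|---|---|---|---|
| Idiopathic | below | no | ACTH test | not cleared | agree |
| Idiopathic | below | yes | ACTH test | cleared | footnote stricter |
| Idiopathic | at or above | no | cleared | cleared | agree |
| Idiopathic | at or above | yes | cleared | cleared | agree |
| Non-idiopathic | below | no | ACTH test | not cleared | agree |
| Non-idiopathic | below | yes | ACTH test | cleared | footnote stricter |
| Non-idiopathic | at or above | no | cleared | not cleared | footnote looser |
| Non-idiopathic | at or above | yes | cleared | cleared | agree |

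The rules disagree in 3 of 8 cases. Listing exactly 7 µg/dL separately gives 2 × 3 × 2 = 12 cases and 4 disagreements, because the looser case then appears twice. These are combinations of rules, not numbers of children.

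**4. Worked example.** A child with organic GHD, no prior HPA assessment, a morning cortisol of 9 µg/dL and no stimulated cortisol passes under footnote 6 or e with no further test. Under 10.1.1 the morning value does not count, and the child still needs a qualifying peak or the ACTH route.

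**5. Does any text rank the two?** None that is visible. The precedence clause in Section 13 covers only the statistical analysis, Protocol against SAP. As context only, the Amendment 1 summary lists the idiopathic restriction as added to the Synopsis and 10.1.1, which would fit footnotes that were not updated. The finding does not depend on that.

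**The case against.** The best case for leaving the text alone has several parts.

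- **The schedules are only an overview.** Section 10.1 describes them that way, which favours 10.1.1 as the detailed rule. But the footnotes do not defer to it: one outcome requires a test and the other settles the matter.
- **The ACTH provision in 10.1.1 is more than discretion.** A test should also be done when results are borderline, not interpretable or raise concerns, and an abnormal sellar MRI could be read as raising concern. This narrows the gap. It does not close it, because a site relying on the footnote has no prompt to look further.
- **There are central and later checks.** The Medical Expert reviews all results before randomization, and morning cortisol is repeated at V1, V3, V4 and V6. Both reduce the risk. Neither says which rule governs, and the repeat is the same measurement that 10.1.1 does not accept on its own outside idiopathic GHD.
- **The group is narrow.** Children assessed earlier, children on replacement under criterion 8 and children with a qualifying stimulated peak fall outside the looser case. This stands.
- **Appendix 1 is redacted.** It may contain further adrenal-test instructions. That cannot be excluded, though it would not make the two visible texts agree.

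A reader might also infer a third conflict at exactly 7 µg/dL. The documents do not support it: the protocol's other unit pairing puts that value at about 194 nmol/L, above the 190 limit.

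**Conclusion.** Wrong as written, and minor. The footnotes and 10.1.1 give incompatible instructions for the same safety check. Only one disagreement matters clinically: the previously unassessed, non-idiopathic child with a morning cortisol at or above the cut-off and no qualifying peak. In the two stricter cases the cost is an extra ACTH test. The documents do not allow the number of children to be estimated.

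Two stronger readings are tempting and should not be drawn. One is that ineligible children would be enrolled. With no cortisol threshold in any numbered criterion, this is a conflict about the adequacy of the work-up, not a breach of an entry criterion. The other is that the treatment comparison is affected. Both arms carry the same footnote wording, and power, alpha and the primary analysis do not depend on it.

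The conclusion assumes that the 10.1.1 rule is the intended one, and that nothing in the redacted appendix overrides the visible text.

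**What to change.** In footnotes 6 and e, make two changes.

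1. Add to the first sentence, after the ACTH requirement:

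> unless a peak cortisol ≥ 500 nmol/L (18 µg/dL) in an insulin tolerance or glucagon test is documented

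2. Replace the second sentence with:

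> 8:00 AM cortisol > 190 nmol/L (7 µg/dL) satisfies the adrenal assessment in subjects with idiopathic GHD only; for other subjects not previously assessed for HPA deficiency, follow Section 10.1.1 (peak cortisol ≥ 500 nmol/L [18 µg/dL] in an insulin tolerance or glucagon test, or a short ACTH test).

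Keep the sentence that allows the assessment within approximately 3 months before Screening.

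The cost is an edit to two sentences in each of two footnotes. A few non-idiopathic children will need the stimulated cortisol that 10.1.1 already calls for. Against that, a child with a documented qualifying peak no longer needs an ACTH test because of a low morning value.

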17.3. Schedule of Events (Genotropin Subjects)

Visit	Screening ^a (-6-0 weeks)	1 ^a (Week 1)	2 (Week 5)	3 (Week 13)	4 (Week 26)	5 (Week 39)	6 (Week 52)
Trial Day (Genotropin subjects)		1 (Predose, Morning)	29-35 (Morning)	85-91 (Morning)	176-182 (Morning)	267-273 (Morning)	365 (Morning)
Visit Window (weeks)				+2	±1	±1	+1
Informed consent	x						
Medical history	x						
Concomitant medication and adverse events		x	x	x	x	x	x
Review of Subject Diary			x	x	x	x	x
Height and weight measurement	x	x	x	x	x	x	x
Physical examination and vital signs ^b	x	x	x	x	x	x	x
Pubertal status	x				x		x
GH-stimulation test(s) ^{c,d}	x						
Assessment of adrenal status ^{e,f}	x						
Karyotype testing ^g	x						
12-lead ECG ^h	x	x			x		
X-ray of left hand and wrist ^c	x						x
Sellar MRI ^c	x						
Fundoscopy ⁱ	x				x		x
Safety laboratory parameters ^j	x	x	x	x	x	x	x
Fasting required	x	x			x		x
Hormone status ^k	x	x		x	x		x
Bioanalytical samples ^l	x	x ^m	x	x	x	x	x
Anti-transglutaminase antibodies ^c	x						
Anti-hGH and anti-PEG antibodies	x ^{n,o}	x ^o	x ^o	x ^o	x ^o	x ^o	x ^o
Drug administration training ^p		x					
Adjustment of dose to body weight				x	x	x	
Study drug administration at site ^p		x ^q					
Postdose vital signs ^b		x ^r					
Injection site reaction assessment		x ^r	x	x	x	x	x

Abbreviations: ECG = electrocardiogram; h = hour; hGH = human growth hormone; MRI = magnetic resonance imaging; PEG = polyethylene glycol; PD = pharmacodynamic; PK = pharmacokinetic

- ^a Following randomization, it is recommended to start V1 within 2 weeks from the time of randomization.
- ^b Vital signs: Heart rate, blood pressure, respiratory rate and body temperature. Subjects should rest for at least 5 minutes before vital sign assessment.
- ^c These diagnostic assessments may be performed prior to Screening within approximately 6 months with proper documentation and approval by the Medical Expert.
- ^d Sex hormone priming suggested (but not required) to be performed in girls over the age of 10 and boys over the age of 11.
- ^e 8:00 AM cortisol (eg, baseline for GH stimulation test) < 7 µg/dL requires an ACTH stimulation test. 8:00 AM cortisol ≥ 7 µg/dL satisfies inclusion. This assessment may be performed prior to Screening within approximately 3 months with proper documentation and approval by the Medical Expert.
- ^f These assessments may be performed prior to Screening within approximately 3 months with proper documentation and approval by the Medical Expert.
- ^g Karyotype evaluation in girls. Results prior to Screening may be accepted if well documented; the final decision rests with the Medical Expert.
- ^h Subjects should rest for at least 2 minutes before ECG assessment. Screening ECG is locally read; all other ECGs to be read centrally.
- ⁱ Should be performed at any time if clinically indicated.
- ^j Hematology (blood smears will be performed locally for back-up analysis), blood chemistry, lipid and glucose metabolism (fasting glucose, insulin, HbA1c, and OGTT can be assessed locally at any time in case of suspicion of glucose intolerance).
- ^k Hormone status: TSH, fT3, fT4, and morning cortisol.
- ^l Bioanalytical samples for hGH, PEG, IGF-1 and IGFBP-3. IGF-1 will be analyzed at Screening and V1 through V6 (excluding V1-2h postdose). hGH and IGFBP-3 will be analyzed at V1 predose through V6; V1-2h postdose sample will only be analyzed for hGH. PEG samples are taken at Screening and V1 predose only, to assist interpretation of anti-PEG antibody data.
- ^m V1: predose and 2 h postdose sample.
- ⁿ The analysis of the anti-hGH and anti-PEG antibodies may only be conducted after randomization and are not required for eligibility verification.
- ^o Analysis for anti-PEG antibodies will only be performed at Screening and V1 (predose) in support of assessment of a trial specific assay cut-point.
- ^p Training on study drug preparation and administration (V1 - during first administration and further as needed).
- ^q Dosing for Genotropin subjects allowed in the morning.
- ^r At 15 min, 1 h, and 2 h postdose.

17.4. PK/PD Sampling and Assessment Schedule for PK/PD subset at Visit 3

Cohort 1 (TransCon hGH)	Days	Time Relative to Dosing						
		1	2	3	4	5	6	7
Blood sampling	Hours	-0.5, 8, 12, 16	24, 36	48	72	96	120	168
ECG	Hours	-0.5, 8, 12, 16	24, 36	48	72	96	120	168
Injection Site Tolerability	Hours	15 min, 1, 2	24					
Vital Signs	Hours	15 min, 1, 2	24					

Abbreviations: ECG = electrocardiogram; hGH = human growth hormone

APPENDICES

- Appendix 1 [REDACTED]
- Appendix 2 [REDACTED]
- Appendix 3 [REDACTED]
- Appendix 4 [REDACTED]
- Appendix 5 [REDACTED]

[Redacted text block containing multiple lines of blacked-out content]

[REDACTED]

[REDACTED]

[REDACTED]

[REDACTED]

[REDACTED]

[REDACTED]

[REDACTED]

[REDACTED]

[REDACTED]

[REDACTED]

[REDACTED]

[REDACTED]

[REDACTED]

[REDACTED]

[REDACTED]

[REDACTED]

[REDACTED]

[REDACTED]

[REDACTED]

[REDACTED]

[REDACTED]

[REDACTED]	[REDACTED]
[REDACTED]	[REDACTED]
[REDACTED]	[REDACTED]
[REDACTED]	[REDACTED]
[REDACTED]	[REDACTED]

[REDACTED]

[REDACTED]

[REDACTED]

[REDACTED]	[REDACTED]
[REDACTED]	[REDACTED]
[REDACTED]	[REDACTED]
[REDACTED]	[REDACTED]
[REDACTED]	[REDACTED]

[REDACTED]

[REDACTED]

[REDACTED]

[REDACTED]	[REDACTED]
[REDACTED]	[REDACTED]
[REDACTED]	[REDACTED]
[REDACTED]	[REDACTED]
[REDACTED]	[REDACTED]

[REDACTED]

[REDACTED]

[REDACTED]

[REDACTED]

[REDACTED]

[REDACTED]

[REDACTED]

[Redacted text block containing multiple lines of blacked-out content]

[Redacted text block]

[Large redacted text block]

[Redacted text block]

[Redacted text block]

[Redacted text block]

[Redacted text block]

[Redacted text block]

3	22-Jan-2019	[REDACTED]	
All the updates in Version 3.0 are further clarifications, rather than changes, in the intended analyses documented in Version 2.0. The updates are finalized by the Ascendis medical and statistical team blinded to study randomization before database lock and unblinding.
 
 • Added detailed criteria to define Per Protocol Population in section 5 • Updated description of data imputation in section 6.1.2 • Added description of mapping post-baseline unscheduled visits and end of study visit in section 6.1.3 • Updated the language in calculations of height SDS and height velocity SDS, and added derivations of age, total duration of treatment (day), total number of planned doses, total actual dosage (mg), and height velocity at baseline in section 6.2 • Updated the language of major protocol deviations in section 7.2 • Updated the language of prior medication definition in section 7.3 • Updated the language in section 8.2 to include height velocity SDS analysis and added description of how Visit 3 will be incorporated for the analyses of IGF-1 /IGF-1 SDS/ IGFBP-3/ IGFBP-3 SDS for the PK/PD population • Updated the language of subgroup analysis and etiology, and extent of GHD subgroup definition in section 8.5, which is also included in detail as Appendix 1 • Updated the language of lab analysis in section 9.2 • Included details for anti-body analysis in section 9.3 • Updated the language of exposure and compliance definitions in section 9.11

4.0	13-Feb-2019	[REDACTED]	
All the updates in Version 4.0 are to address FDA’s comments received on 25 Jan 2019
 
 • Updated the language of ITT definition in Section 5 • Removed LOCF imputation for numeric and categorical variables, and added non-responder imputation for categorical variables in Section 6.1.2 • Clarified the primary analysis for the primary endpoint is the MMRM model after retrieved dropout imputation in Section 8.1 • Removed testing of IGF-1 as part of hypothesis testing in Section 8.2 • Updated the language in Section 8.3 regarding how to calculate average IGF-1 SDS at Week 52 • Removed testing of IGF-1 in the multiplicity control section in Section 8.6
